Research Protocol

A randomized, placebo-controlled, double-blind, parallel-group study of the effects of nicotinamide mononucleotide on body composition in elderly men

Principal Investigator: [name]

The University of Tokyo Hospital, Department of Diabetes and Metabolism

Address: [name]

[contact]

[contact]

E-mail address: [contact]

Emergency contact: [name]

Planned period of clinical research implementation:

After approval by the Ethics Committee - December 2023

Registration period:

After Ethics Committee approval - December 2019

Clinical Study

A randomized, placebo-controlled, double-blind, parallel-group study of the effect of nicotinamide mononucleotide (NMN) on body composition in elderly men.

Research Protocol

1. Background of the study

A rapidly aging population highlights the need to maintain good physical and mental health in elderly people. Nicotinamide adenine dinucleotide (NAD⁺)-dependent deacetylases sirtuins have received growing attention as longevity genes. Preclinical studies have shown that activation of sirtuins delays the inevitable decline in physiological functions that occur with aging (e.g., muscle strength and immunity to disease).^{1,2,3} It is hypothesized that preventing the age-dependent decline in NAD⁺ levels would prolong the normal physiological function in humans⁴. Given that NAD⁺ is generally not permeable to cell membranes, it is substituted by nicotinamide mononucleotide (NMN) and nicotinamide riboside (NR), two of its precursors, during intervention studies. NMN is a vitamin B3 analog, which is sold and consumed in foods and supplements. At present, there is insufficient clinical evidence supporting the efficacy of NMN ingestion on physiological markers of aging. The proposed clinical trial is a randomized, placebo-controlled, double-blind, parallel-group study of the effects of NMN intake on physiological indicators of aging including body composition changes in healthy elderly men. This study is equivalent to an exploratory study.

[figure not shown]
2. Objectives of the study

The purpose of this study is to determine the efficacy of NMN intake by comparing the body composition of NMN-treated and placebo-treated elderly men.

3. Outline of the food

3.1 Food Information

Food name: Nicotinamide mononucleotide (structural formula: see figure).

Dosage form: tablet.

Source of the food: Mitsubishi Corporation Life Sciences Limited, Tokyo, Japan.

Storage method: refrigeration.

3.2 Anticipated adverse reactions due to participation in the study

Allergic symptoms, gastrointestinal symptoms (e.g., diarrhea), facial flushing, liver damage.

4. Eligibility

Healthy elderly people who meet the following criteria (recruitment is entrusted to Newing NPO Corporation, Tokyo, Japan) are eligible for the study.

4.1 Selection criteria

- 1) Individuals who have received sufficient explanations regarding participation in this study and have given their free written consent with full understanding.
- 2) Males aged 65 years or older at the time of obtaining consent.
- 3) Participants with a body mass index (BMI) between 22 and 28.
- 4) Non-smokers.

4.2 Exclusion criteria

- 1) Individuals who consume healthy foods or supplements that may affect the research (e.g., NMN, NR, resveratrol, niacin, and nicotinamide).

- 2) Individuals who have been continuously exercising for at least 1 h every day for at least six months.
- 3) Individuals with a history of malignancy, heart failure or treatment for myocardial infarction.
- 4) Individuals diagnosed with any of the following chronic diseases: atrial fibrillation, arrhythmia, hepatic disorder, renal disorder, cerebrovascular disorder, rheumatism, diabetes, dyslipidemia, hypertension, and other chronic diseases.
- 5) Individuals who regularly use medicines (including herbal medicines).
- 6) Individuals with allergies to pharmaceuticals or test food-related foods.
- 7) Individuals currently participating in other clinical research/trials or have participated in other clinical research/trials within the past 3 months.
- 8) Other participants judged by the investigator as inappropriate for this study.

Rationale for setting exclusion criteria: 1–2, impact on efficacy assessment; 3–7, safety considerations.

5. Explanatory information and consent form for research participants

The explanatory and consent documents are approved by the Ethics Committee and given to research participants; their free and voluntary consent is obtained in writing after sufficient oral and written explanation is provided.

Research participants are promptly notified when information on efficacy and safety that may affect their consent emerges; their willingness to continue or withdraw from the study is confirmed. Research participants are promptly notified of any changes to the research plan that may affect their consent, and their intention to participate in the research is confirmed in advance.

The consent document should be prepared in three copies: one copy is sent to the Clinical Research Support Center for safekeeping, the other copies are for the research participants and the department.

If research participants or their families wish to receive information or consultations about the research, they should contact their physician or the Clinical Research Support Center.

The following 18 items are included in the explanatory and consent documents:

1. Introduction: overview of clinical research.
2. Purpose of the study.
3. Methods used in the study.
4. Expected duration of participation in the study.
5. Expected number of participants in the study.
6. Anticipated benefits and possible disadvantages of participation in the study.
7. Available alternative treatment options if one does not participate in the study.
8. Any damage to one's health that may occur during the study.
9. Participation in the study is of anyone's own free will.
10. Information about the study will be communicated to participants as needed.
11. The research may be discontinued at any time.
12. Participation in the study implies that participants' medical records and other information may be examined during or after the study.
13. Even if the results of the study are made public, participants' identity will not be revealed.
14. What participants must do if they agree to participate in this study.
15. Participants' cost burden.
16. Intellectual property rights and conflict of interest.
17. Physician in Charge.
18. Consultation Service.

6. Research methods

6.1 Approval by the Ethics Committee and other bodies

The principal investigator shall have the research protocol, explanatory documents, and consent documents reviewed by the Ethics Committee and obtain permission for implementation by the hospital director.

6.2 Type and design of the study

Type of control: placebo-controlled.

[figure not shown]
Characteristics of the design: parallel-group.

Randomization: yes.

Blinding: double-blind.

Exploratory clinical study.

6.3 Outline of the study (see the flowchart)

6.4 Expected duration of participation in the study

Minimum 13 weeks; maximum 16 weeks.

Minimum observation period: 1 week; maximum observation period: 4 weeks; duration of treatment: 12 weeks.

The follow-up period is not included in the study period.

6.5 Food dosage and administration period

Oral intake of 250 mg NMN or placebo for 12 weeks.

There have been several reports of NMN administration to mice via intraperitoneal or oral routes at doses of 100–500 mg/kg/day¹. In particular, in long-term experiments, whereby NMN was administered at doses of 100 or 300 mg/kg/day for 1 year, no significant adverse side effects were observed². Taking into account the absorption area of the small intestine, 100 mg/kg/day of NMN in mice is equivalent to 8 mg/kg/day of NMN in humans². In an oral acute toxicity test on rats conducted by Mitsubishi Corporation Life Sciences Limited. , no particular problems were observed at a dose of 2000 mg/kg/day. Even though there are no reports of NMN administration in humans, three clinical studies have been registered in Japan and one in the United States. The latter (ClinicalTrials.gov Identifier: NCT03151239) foresees a dose of 250 mg/day for 8 weeks, and one of the Japanese studies (UMIN Study ID UMIN000025739) envisions a dose of 100 or 200 mg/day for 24 weeks. In the case of NR, several clinical studies in humans have been reported, with doses of 100–2000 mg/day administered for up to 12 weeks causing no serious side effects⁴. In long-term NR administration experiments in mice, a dose of 400 mg/kg/day was administered for 12 weeks³. Based on the above experimental evidence, there is no significant difference between the effective dosage of NMN (100–300 mg/kg/day) and NR (400 mg/kg/day) in mice. The dose chosen in the present study was set in consideration of the doses used in the abovementioned clinical trials (100, 200, and 250 mg/day).

6.6 Dosage form and food ingredients

Dosage form: tablet (250 mg NMN in 6 tablets).

NMN food ingredients: NMN, maltitol, crystal cellulose, silicon dioxide, magnesium stearate, flavor (food additive).

Placebo component: maltitol, crystal cellulose, silicon dioxide, magnesium stearate, flavor (food additive).

6.7 Provisions for concomitant medication

Individuals who regularly use pharmaceutical products are excluded from the study.

6.8 Procedures for the management and delivery of food

The person in charge of assigning the study foods will enter placebo or NMN food numbers on the study food assignment sheet at Mitsubishi Corporation Life Sciences Limited., and store the food without disclosing its identity to others until the end of the study. The food will be delivered by Mitsubishi Corporation Life Sciences Limited. to the principal investigator, who will keep it refrigerated. The food will be provided to the participants at the time of the interview.

6.9 Instructions regarding food intake

Time of intake: after breakfast.

Method of intake: oral intake.

Administration in case of forgotten intake: daily intake after breakfast is preferable, but in case of forgotten intake, it can be taken at any time during the day.

Storage and return of leftover medication and containers: food is to be stored in a cool place away from direct sunlight, high temperature, and humidity. Any leftover food will be returned at the end of the study.

Research participants will be instructed not to change their exercise habits before and after the start of the study.

6.10 Case enrollment and allocation procedure

Research participants who meet the selection criteria (4.1) but do not fall under the exclusion criteria (4.2) are confirmed as eligible for the study. The principal investigator or study collaborator will fill in the necessary information on the registration form and send it to the third-party company responsible for allocation (C&C QUALITAVE RESEARCH INSTITUTE INC. Tokyo, Japan.; Manager: [name]). The company responsible for the allocation will confirm the contents of the registration form and assign a food number. Confirmation of the registration form with the food number will be sent to the University of Tokyo Hospital.

1) Among research participants who have expressed their willingness to participate in this study, those who have given written informed consent will be selected based on the results of the medical interview and blood test, and will be listed on the registration form as study participants and assigned a registration number.

2) The randomization of food intake will be conducted by a third-party company responsible for allocation (C&C QUALITAVE RESEARCH INSTITUTE INC.) using the registration number on the registration form. The randomization procedure will not involve the University's researchers, the principal investigator, or Mitsubishi Corporation Life Sciences Limited., and will not be disclosed until the end of the study.

Allocation criteria:

- a. Age should not differ significantly between groups.
- b. Skeletal muscle mass index (SMI) and BMI should not differ significantly between groups.

6.11 Actions taken after completion of the study

After completion of the study, research participants will return to their habitual dietary habits and no special measures will be taken.

6.12 Preservation of samples obtained from human participants and information used in the research

1) Anonymization of samples and storage method

After samples are obtained, they will be promptly anonymized by deleting any personal identifiers, such as names and registration IDs; instead, a research identification number will be attached. The anonymized samples will be measured immediately or stored at the P1 Unit, University of Tokyo Hospital, where access privileges are restricted by a locked door, at -80°C until the end of the study. After the measurement is completed or the storage period has elapsed, the identification number will be deleted by cutting the identification label, and the samples will be disposed of.

2) Anonymization of information and storage method

After the information is obtained, it will be anonymized by immediately deleting any personal identifiers, such as names and medical record IDs, and will be replaced by a research identification number. A correspondence table that can be linked to personal information will be created. The anonymized information and the correspondence table will be held in the laboratory of the person in charge of management (A501 and 618, Clinical Research Building, University of Tokyo Hospital) in separate storage rooms with locked and restricted access.

3) Storage period and disposal method

Information related to this research will be stored for 5 years from completion of the study or three years from the final publication of the study results, whichever is later, and then disposed of in an unrecoverable form by shredding the printed media or deleting the electronic files.

7. Evaluation items

Primary endpoint: change in SMI measured by bioelectrical impedance analysis (BIA).

Secondary endpoints: changes in markers of physiological aging determined by: (1) physical measurements, (2) blood tests, (3) physiological tests, (4) radiological examination, (5) questionnaires, and (6) diary.

Correlations between blood concentrations of NAD-related metabolites, including NAD, nicotinamide, nicotinic acid (NA), NR, NAR, nicotinic acid mononucleotide (NAMN), nicotinic acid adenine dinucleotide (NAAD), tryptophan, methyl nicotinamide, quinolinic acid, glutathione, adenosine monophosphate (AMP), adenosine diphosphate (ADP), and adenosine triphosphate (ATP), before intake and measured aging markers will be evaluated.

7.1 Body measurements

Height, weight, body composition (BIA method), waist circumference, lower leg circumference, blood pressure, heart rate, grip strength, visual test, hearing test, 30-s chair stand test, and gait speed.

*Height is measured only during pre-treatment screening.

7.2 Blood tests

1) Hematological examination

White blood cell count, red blood cell count, hemoglobin, hematocrit level, platelet count, average red blood cell pigment content, average red blood cell volume, and average red blood cell pigment concentration.

2) Blood biochemical tests (including safety endpoints)

Triglyceride, total cholesterol, LDL-cholesterol, HDL-cholesterol, glucose, HbA1c, insulin, serum c-peptide (CPR), aspartate transaminase (AST), alanine aminotransferase (ALT), gamma-glutamyl transferase (γ -GTP), creatine kinase (CK), total protein, albumin, uric acid, uric acid nitrogen, creatinine, sodium, potassium, hormone tests (free testosterone, testosterone, dehydroepiandrosterone sulfate [DHEA-S], osteocalcin, pentosidine, and adiponectin), interleukin-6 (IL6), and NAD metabolism-related metabolites (NAD, NMN, nicotinamide, NA, NR, NAR, NAMN, NAAD, tryptophan, methyl nicotinamide, quinolinic acid, glutathione, AMP, ADP, and ATP).

3) 75 g oral glucose tolerance test (75g OGTT)

Performed at 0 min, 30 min, 60 min, and 120 min; it will measure blood glucose, insulin, and serum-CPR.

7.3 Physiological tests

Assessment of vascular endothelial function by the flow-mediated dilation (FMD) test and bone density test.

7.4 Radiological examination

Evaluation of visceral fat and fatty liver by computed tomography (CT).

7.5 Questionnaires

Common questionnaire about dietary behavior and anti-aging QOL, Mini-Mental State Examination-Japanese (MMSE-J), and Japanese version of Montreal Cognitive Assessment (MoCA-J). *MMSE-J and MoCA-J are administered only at week 0 and week 12.

7.6 Daily diary

During the intake period, the presence/absence of test food intake, physical condition, and dietary survey will be recorded daily in a designated diary.

8. Observation and test items, methods of data collection

Schedule				
items	Screening	Baseline	Supplement period	
Period	1-4weeks before	Week 0	Week 6	Week 12
Visit	1	2	3	4
Obtaining consent	○			
Background	○			
Supplement intake		←—————→		
Subjective symptoms	○	○	●	●
Confirmation of adverse events	←—————→			
Vital signs	○			●
Body measurements	○			●
Blood test 1	○			●
Blood test 2		○		●
75g OGTT		○		●
FMD test		○	●	●
Bone density test		○		●
Radiological examination		○		●
Questionnaires		○	●	●
Diary		←—————→		

Items marked with ○ are to be assessed before the start of supplements intake.

Items marked with ● are to be assessed after the start of supplements intake.

- 1) Background: gender, date of birth, height, weight, and medical history.
- 2) Supplements intake: record of start and end dates.
- 3) Subjective symptoms and other findings: to be confirmed by interview or other means.
- 4) Confirmation of adverse events and side effects: adverse events include various laboratory abnormalities.

The nature, timing of onset and disappearance, degree, treatment, outcome, evaluation of severity, and relationship to the study drug should be described in the medical record and case report. Follow-up studies should be conducted if necessary. The severity of the disease will be defined as 1) mild: the patient can continue the trial without treatment, 2) moderate: the patient can continue the trial with some treatment, and 3) severe: the patient should stop or discontinue the trial. Serious adverse events are defined on a scale of 10 and should be reported promptly if applicable.

5) Vital signs: blood pressure, pulse rate, respiratory rate, body temperature, and oxygen saturation.

6) Body measurements: height, weight, body composition (BIA method), waist circumference, leg circumference, grip strength, visual test, hearing test, 30-s chair stand test, and gait speed.

*Height is measured only during pre-intake screening.

7) Blood test 1: CK, total protein, albumin, uric acid, blood urea nitrogen (BUN), creatinine, sodium, potassium, as well as immunobiological tests for HBs antigen, HCV antibody, HIV antibody, and syphilis (STS and TPHA).

8) Blood test 2: CRP, hormone tests (free testosterone, testosterone, DHEA-S, osteocalcin, pentosidine, and adiponectin), IL6, NAD metabolism-related metabolites (NAD, NMN, nicotinamide, NA, NR, NAR, NAMN, NAAD tryptophan, methyl nicotinamide, quinolinic acid, glutathione, AMP, ADP, and ATP). About 5 mL of whole blood is sent frozen to the Department of Metabolism and Nutrition, Graduate School of Medicine and Pharmaceutical Science for Research, Toyama University, for measurement using a mass spectrometer. After measurements, the sample will be destroyed and the data will be sent to the principal investigator.

9) 75g OGTT at 0 min, 30 min, 60 min, and 120 min; measuring blood glucose, insulin, serum-CPR.

10) FMD test.

11) Bone density test: performed using a bone densitometer.

12) Radiological examination: abdominal CT scan.

13) Questionnaire: common questionnaires about food attitude and anti-aging QOL, MMSE-J, and MoCA-J. *MMSE-J and MoCA-J are administered only at week 0 and week 12.

14) Diary: during the intake period, the participants' physical condition and dietary survey will be recorded daily in a designated diary.

On each visit, the patient will be asked to come to the hospital with a fasting breakfast and no test food intake to perform the test properly.

9. Discontinuation criteria

The following criteria will be considered grounds for discontinuing the research.

- 1) If the research participant declines to participate in the research or withdraws consent.
- 2) If the eligibility of the participant is found to be no longer valid after enrollment.
- 3) If it is difficult to continue the research due to adverse events.
- 4) If the entire study is discontinued.
- 5) If the physician deems it appropriate to discontinue the research for any other reason.

If the principal investigator and sub-investigators determine that it is impossible to continue the study for any reason, the date, reason, and course of discontinuation/withdrawal will be clearly stated in the medical record and case report, and necessary tests will be conducted at the time of discontinuation/withdrawal to evaluate efficacy and safety.

In the case of discontinuation due to an adverse event, treatment or follow-up observation should be conducted until the patient recovers as much as possible to the original state.

10. Handling in the case of an adverse event

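### Section 8 assigns the liver enzymes and blood count listed in section 7.2 to no visit, although section 3.2 anticipates liver damage

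*Protocol*

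**What the plan says.** Section 3.2 of the protocol gives the anticipated reactions as "Allergic symptoms, gastrointestinal symptoms (e.g., diarrhea), facial flushing, liver damage".

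Section 7.2 lists the blood tests of the trial. Its haematology item begins "White blood cell count, red blood cell count, hemoglobin, hematocrit level, platelet count" and goes on to the red-cell indices. Its second item is headed "Blood biochemical tests (including safety endpoints") and contains, among others, "aspartate transaminase (AST), alanine aminotransferase (ALT), gamma-glutamyl transferase".

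Section 8 says what is drawn and when. Item 4 reads "Confirmation of adverse events and side effects: adverse events include various laboratory abnormalities". Item 7 defines "Blood test 1: CK, total protein, albumin, uric acid, blood urea nitrogen (BUN), creatinine, sodium, potassium", followed only by infection serology. Item 8 defines "Blood test 2: CRP, hormone tests (free testosterone, testosterone, DHEA-S, osteocalcin, pentosidine, and adiponectin), IL6", followed by the NAD-related metabolites. Item 9 defines "75g OGTT at 0 min, 30 min, 60 min, and 120 min; measuring blood glucose, insulin, serum-CPR".

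In the section 8 schedule, vital signs and Blood test 1 are marked at screening and Week 12. Blood test 2 and the OGTT are marked at Week 0 and Week 12. Week 6 has subjective symptoms, FMD and questionnaires, with adverse-event confirmation and the diary running throughout.

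**The concern.** Section 8 is the part of the protocol that site staff follow when they order tests. If its panels leave out a safety test that section 7.2 promises, the test depends on someone noticing the gap. The omission falls on the anticipated reaction that most depends on a blood test, because a rise in liver enzymes can be silent.

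Under a literal reading there would be neither a pre-dose nor a Week 12 enzyme value, so a laboratory adverse event of this kind could not be recognised or compared between groups. Section 6.5 says that no administration of NMN to humans has been reported, so the trial's own safety data carry weight.

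The screening step is touched as well. Section 6.10 selects participants partly on a blood test, and section 4.2 excludes men diagnosed with hepatic disorder, dyslipidemia or diabetes. The screening panel as defined contains no liver enzymes, lipids, glucose or HbA1c.

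**Working it through.** The protocol states no figure for this point. The check is a count of the 7.2 analytes against the panels in section 8, items 7 to 9. The NAD-related metabolites are left out of the count because they are research assays; all of them are in Blood test 2. The item that 7.2 calls uric acid nitrogen is taken to be the BUN of item 7.

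| Group in 7.2 | Listed | Blood test 1 | Blood test 2 | OGTT | No visit |
|---|---|---|---|---|---|
| Haematology | 8 | 0 | 0 | 0 | 8 |
| Triglyceride and three cholesterol measures | 4 | 0 | 0 | 0 | 4 |
| Glucose, HbA1c, insulin, C-peptide | 4 | 0 | 0 | 3 | 1 (HbA1c) |
| AST, ALT, gamma-GTP | 3 | 0 | 0 | 0 | 3 |
| CK, total protein, albumin, uric acid, BUN, creatinine, sodium, potassium | 8 | 8 | 0 | 0 | 0 |
| Six hormone-test markers and IL6 | 7 | 0 | 7 | 0 | 0 |
| Total | 34 | 8 | 7 | 3 | 16 |

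Listed: 8 + 26 = 34. Assigned to a visit: 8 + 7 + 3 = 18. Not assigned: 34 − 18 = 16.

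The count is robust to two doubtful spellings. If uric acid nitrogen were not BUN, the unassigned number would be 17. If CRP in item 8 were a slip for CPR, nothing would change, because CPR is already counted under the OGTT.

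Visits at which section 8 measures AST, ALT, gamma-GTP or a blood count: 0 of 4.

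**Why a truncated list is likely.** In 7.2 the biochemistry runs from lipids through the glucose-related items to AST, ALT, gamma-GTP and then CK. Item 7 of section 8 begins at CK and keeps the same order to potassium. The unassigned items all stand before CK in 7.2, which fits a list that has lost its opening.

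**Week 6.** The rows for subjective symptoms, FMD and questionnaires keep their Week 6 marks, so a damaged table is an unlikely explanation for the empty cells elsewhere. Blood pressure and heart rate also appear under body measurements in 7.1, but that row too is marked only at screening and Week 12. Scheduled vital signs or blood draws after the first dose and before Week 12: none. The longest stretch of dosing without such a check is 12 × 7 = 84 days; with a Week 6 check it would be 6 × 7 = 42 days. These figures describe the calendar only, because the protocol gives no event rate.

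**The case against.** The strongest reply is that section 8 should not be read alone. Section 7.2 lists the tests, section 7 makes changes in blood-test markers secondary endpoints, and section 14.2 handles those like the primary endpoint, which is Week 12 minus baseline. Section 6.10 uses a blood test for selection. Together these show that pre- and post-intake values were intended. This stands, and it limits the point: a reader might infer that the trial would go without liver enzymes, and the documents do not support that. They support only that section 8, followed as written, does not call for them. A line lost from the published file cannot be wholly excluded, although item 7 reads as a complete sentence.

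On Week 6, a reader might infer that the empty cells are an error or a breach of the plan. No passage promises Week 6 laboratory tests, and counting laboratory abnormalities as adverse events sets no testing frequency. The men have no chronic disease or regular medication. There is a symptom interview at Week 6, a daily diary, continuous adverse-event confirmation, follow-up where needed and testing on discontinuation.

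Section 6.5 also cites reassuring data: mice dosed for 1 year, a rat acute test at 2000 mg/kg/day, and human experience with NR up to 12 weeks. It equates 100 mg/kg/day in mice to 8 mg/kg/day in humans. For an assumed weight of 60 to 70 kg that is 480 to 560 mg/day, about twice the 250 mg given. All of this stands, and it makes the Week 6 panel a design judgement. What it does not supply is a guaranteed test for a symptom-free change during dosing.

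**Conclusion.** Section 8 is inconsistent with sections 3.2 and 7.2 and should be corrected. Sixteen of 34 routine analytes, including all three liver enzymes and the whole blood count, are assigned to none of the four visits. The count rests on taking uric acid nitrogen as BUN and on item 7 being complete as published. A drafting slip is the likely origin, and the tests were probably intended.

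The absence of vital signs and blood tests between the first dose and Week 12 is a secondary matter: a cheap improvement worth considering, and no error in the plan. The risk to participants is probably low on the evidence that the protocol cites. The effect is on participant safety and on the safety conclusion. The primary SMI comparison is not affected.

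**What to change.** **Needed.** In section 8, item 7, start the Blood test 1 list with the blood count, the four lipids, HbA1c, AST, ALT and gamma-GTP, then continue from CK as now. The schedule then gives each of them a value at screening and at Week 12. No extra needle stick is required, because Blood test 1 is already drawn at both visits. The cost is a protocol amendment and up to 42 × 2 = 84 sets of routine assays, plus those for men who fail screening. If the list was merely truncated, these assays were planned anyway and only the wording changes.

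**Optional.** At the existing Week 6 visit, which participants already attend fasting, mark vital signs and a short panel: AST, ALT, gamma-GTP, CK, creatinine, sodium, potassium and blood count. Name the analytes, so that the infection serology in Blood test 1 is not repeated. With the first change made, each Week 6 value has a pre-dose and a Week 12 value beside it, and section 14.2 already provides for comparisons 6 weeks after intake. The cost is about 42 routine draws, one per man, and the laboratory charge.
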